A Preliminary Study of Sublingual Fentanyl for the Management of Breakthrough Pain Analgesia in Patients with Advanced Cancer

Principal investigator: [name]

Co-principal investigator: [name]

Supportive Care Co-investigator: [name], [name], [name]

Biostatistics Co-investigator: [name]

Table of Contents

A. Study Objectives	2
B. Background.....	2
C. Experimental Approach	2
D. Statistical Analysis	11
E. Data Confidentiality Procedures.....	12
F. References.....	14

A. Study Objectives

Primary objective: To determine the **effective dose** of fentanyl sublingual spray (FSS) in the management of breakthrough pain in hospitalized patients with advanced cancer receiving continuous opioid infusion and seen by the palliative care team (consultation service or palliative care unit).

Secondary objective #1: To estimate the differences in the **pain response between intravenous opioid** breakthrough and FSS at effective dose.

Secondary objective #2: To determine the safety, tolerability, pattern of use, and efficacy of FSS in patients with advanced cancer during the first month post-hospital discharge.

B. Background

More than 80% of patients develop cancer pain before they die [1]. The vast majority of these patients are receiving opioid analgesics until the time of their death [2]. Pain in cancer patients can be constant interspersed with breakthrough pain episodes. Breakthrough pain is defined as “a transient exacerbation of pain that occurs either spontaneously, or in relation to a specific predictable or unpredictable trigger, despite relatively stable and adequately controlled background pain.”[10] There are at least 4-5 episodes of BT pain in cancer patients per day [3, 4]. The treatment of cancer pain consists of providing opioid analgesia on a constant basis. However BT episodes are not typically covered by scheduled analgesics. Hence short acting opioids are useful for these settings. However, most available opioids do not peak in activity and match the onset and duration of BT episodes. Unfortunately, the great majority of patients develop difficulties with swallowing before death. This is due to a number of factors including delirium, dysphagia, bowel obstruction, and emesis.

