The commercial supply of study medication will be provided by Insys Therapeutics Ltd. FSS was FDA approved in 2012 for “For the management of breakthrough pain in adult cancer patients who are already receiving and who are tolerant to around-the-clock opioid therapy for their underlying persistent cancer pain.” This study consists of two stages:

Stage 1. In-hospital pain management. Once patients are enrolled, our research nurse will be notified to provide careful instructions on medication use. Patients will be monitored for 3 episodes of breakthrough pain (Figure 1).

(1) First episode – patients will be given a single dose of breakthrough opioid from their existing PCA pump that is equivalent to 10% of their MEDD. The dose used in this study is consistent with our routine clinical practice. Immediately upon patient enrollment, the study physician will be notified and will determine the morphine equivalent daily dose (MEDD) in real time using standardized

equianalgesic ratios. We will then determine the doses of intravenous opioid needed (i.e. 10% of MEDD as per standard of care). For example, a patient had a MEDD of 200 mg/day at the time of enrollment. The IV opioid dose will be morphine 8mg IV x1 dose (or equivalent).

(2) Second episode

- a. The patient will be given a single dose of FSS that is equivalent to 16-32% of their MEDD (Table 2). Because FSS is available in fixed dosage forms, the actual % of MEDD will be determined. Pain intensity will be assessed at 30 minutes. A breakthrough pain intensity reduction of $\geq 2/10$, $\geq 33\%$ of baseline pain intensity, reduction of pain intensity to personal pain goal (PPG) score or below, OR absolute value below background pain level will be considered as an effective dose.
- b. If breakthrough pain not effective at 30 minutes, the patient will repeat the same dose one more time (with a cap of 1600 mcg total; i.e. dose given 30 minutes ago + dose now = 1600 mcg maximum), and their pain intensity will be reassessed over the next 30 minutes again.

(3) Third episode (at least 4 hours after second episode)

- a. If the patient required 2 breakthrough FSS doses for the last episode of breakthrough pain, or if the effective dose has not been identified, he/she will double the last administered dose, and pain intensity will be assessed at 30 minutes.

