- b. If breakthrough pain not effective at 30 minutes, the patient will repeat the same dose one more time (with a cap of 1600 mcg total; i.e. dose given 30 minutes ago + dose now = 1600 mcg maximum), and their pain intensity will be reassessed over the next 30 minutes again.

(4) The study assessments will be conducted Monday to Friday between 8AM and 4PM in the institution while under the supervision of our research nurse. Outside of this window, patients will need to use regularly prescribed breakthrough medications.

(5) While we expect a majority of patients will be able to identify an effective dose within the first 2 episodes of breakthrough pain, some patients may be discharged or their opioid infusion may be discontinued before an effective dose is identified. If that is the case, then their data will be censored for the primary objective.

(6) Once the effective dose is found, the first stage of this study is complete and they will no longer be on FSS. Patients who have identified an effective FSS dose may proceed to the next stage of this study upon discharge.

(7) We are limiting the total number of episodes to minimize attrition, minimize variability in basal opioid doses, and also because we are using an accelerated titration process so many patients will be starting already at higher doses than in the outpatient setting.

Table 2. FSS Dose for Breakthrough Pain Episode Based on Morphine Equivalent

Daily Dose

Morphine equivalent daily dose (mg)	FSS (mcg) starting dose	FSS starting dose % equivalent of MEDD	Titration schedule while in hospital (if effective dose already identified, there will be no need to titrate upwards)
70-109	100	16.1-25.0%	100/100 – 200/200
110-219	200	16.0-31.8%	200/200 – 400/400
220-289	300	18.2-23.9%	300/300 – 600/600
290-379	400	18.5-24.1%	400/400 – 800/800
380-469	500	18.7-23.0%	500/500 – 1000/600
470-579	600	18.1-22.3%	600/600 – 1200/400
580-669	700	18.3-21.1%	700/700 – 1400/200
670-750	800	18.7-20.9%	800/800 – 1600/NA

For intravenous opioid, the medication will be given by the research nurse or bedside nurse via the infusion pump. FSS will be provided by Dispensing Pharmacy. After providing careful instructions, the research nurse will keep the spray with the patient for ease of administration.

The following instructions will be given to the patient:

1. Swallow any saliva in your mouth.
2. Hold the medication spray unit upright using your index and middle fingers and thumb.

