⁸ Patient global impression will be documented by the question "after starting your new treatment, how are your symptoms (i.e. pain)?" This has been used in multiple previous studies to assess patient perceived change.[11, 12] We will also ask patients which treatment (intravenous/spray/don't know) they prefer.

⁹ if a repeat FSS dose is needed

¹⁰ Breakthrough pain episode #3 will only be assessed if the patient did not achieve an effective dose after the first FSS dose

Table 4. Summary of Study Assessments during Stage 2

	Days 1-28 post discharge
Average pain intensity over last 24 hours ¹	Daily
Use of FSS ²	Daily
Pain medication and doses ³	Daily
Adverse effects ⁴	Daily
Complications ⁵	As they occur
Karnofsky Performance status ⁶	Weekly
Ease of use and perceived effectiveness ⁷	Weekly
Satisfaction with breakthrough opioid use ⁸	Weekly
Study satisfaction ⁹	End of study once

¹ a 0-10 numeric rating scale that assesses average pain intensity over the past 24 hours, where 0= no pain at all, and 10=worst possible.

² The number of BTP episodes and doses of FSS used per day will be documented. The duration of BTP episodes will also be recorded.

³ all opioid use (name, dose, frequency, and use of breakthroughs) during this stage, including the need for any dose escalation/reduction, will be recorded. Use of other pain medications such as acetaminophen, NSAIDs, steroids will also be documented.

⁴ adverse effects related to the use of opioids, such as dizziness, drowsiness, nausea, vomiting, anxiety, itching/sneezing, taste disturbance and constipation will be assessed using a numeric rating scale from 0-10 to assess the average intensity of last 24 hours.

⁵ the dates and reasons for acute complications such as re-admission, emergency room visits and falls will be recorded as they occur

⁶ an 11-point assessment scale that rates patients' functional status between 0% (death) and 100% (completely asymptomatic) based on their ambulation, activity level, and disease severity³⁷. A patient self-rated version will be used.

⁷ Ease of use and perceived effectiveness will be assessed using a 0-10 numeric rating scale

⁸ Satisfaction with breakthrough opioid use will be assessed by asking "How satisfied were you with the sublingual spray medication, taking the side effects, logistics and pain control into account? 0-10".

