Regulatory monitoring will be provided by the principal investigator, the Institutional Review Board (IRB), and the Data Safety and Monitoring Board (DSMB). Patient confidentiality will be ensured by use of study numbers, secure storage of clinical data, and anonymous reporting.

D. Statistical Analysis

D.1. Power Calculation. This investigator-initiated, single arm, open-label study will enroll a total of 30 hospitalized patients. Considering an attrition rate of 25% for the reasons of but not limited to consent withdrawal, early drop-out or primary endpoint not achieved, etc, 22 patients are expected to be treated with FSS and reach the effective dose measured as % MEDD dose. We expect to enroll approximately 2-3 patients per month for this study. Thus, we expect to complete the study in approximately 10-12 months.

The primary objective is to determine the effective dose of FSS for powering future studies. After being enrolled, each patient will be treated with intravenous opioid for the first episode of breakthrough pain and up to two more episodes treated with FSS for the purpose of the primary objective. If the effective dose is not found after a total of three episodes, patients will be considered inevaluable for the primary objective. With 22 evaluable patients, a two-sided 95% confidence interval for %MEDD of effective dose will extend 2.1%, 4.2%, 6.3% or 8.4% from the observed mean, if the standard deviation

is 5%. 10%, 15% or 20% and the confidence interval is based on the large sample z statistic.

Table 5. Sample Size Justification

Standard Deviation	5%	10%	15%	20%
Confidence Interval	2.1%	4.2%	6.3%	8.4%

At the end of the study we will summarize the effective dose of FSS measured by % MEDD dose using descriptive statistics such as mean, standard deviation, and 95% confidence interval. The pattern of FSS effective dose such as episodes and number of doses will be summarized by tabulation. It is also important to estimate percentage of patients who have been treated with FSS however did not reach the effective dose. We will provide detailed description of reasons of drop-out.

Secondary endpoints include the differences in the pain response between intravenous opioid breakthrough and FSS at effective dose, safety, tolerability and pattern of FSS use, and efficacy of FSS during the first month post-hospital discharge.

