D.2. Data Analysis. Summary descriptive statistics will be provided for demographics, outcomes, concurrent opioids, various physiological parameters, and other collected variables such as the changes of pain score after each episode, neurocognitive testing and digital substitution, overall preference and global impression, ease of use and perceived effectiveness, satisfaction with breakthrough opioid use and study satisfaction by using proportions, medians, means, 95% confidence intervals, and other statistics as appropriate for the measure. Each endpoint may be evaluated repeatedly at each episode and during the first month post-hospital discharge. Repeated measures analysis may be employed to evaluate the change of these measures over time. The effect of treatment on the changes of these measures will also be estimated in the same model when possible. Other statistical analysis may be employed when appropriate.

E. Data Confidentiality Procedures

Health information will be protected and we will maintain the confidentiality of the data obtained from the patient's chart.

Collection of identifiers: We will collect and securely store patients' identifiers (including name, medical record number, and demographic specifications). Each patient will be assigned a study number that will be the only identifier to figure in the analytical file and personal data will not be disclosed in any form. The key linking these numbers will be retained in a securely locked file by the investigator.

Data Storage: Protection of electronic and paper records will be guaranteed. All electronic records will be stored on password-protected institution computers behind the institution firewall. Any paper records will be classified and stored in locked files inside a locked office.

Training of personnel: Only MDACC personnel trained in maintaining confidentiality, the principle investigators and co-investigators, will have access to study records.

Data sharing: Study data will not be shared with any individuals or entities. The data will be kept by the principle investigator in a locked file cabinet.

Final disposition of study records: These data will be used only for this research study data files will be destroyed 5 years after publication of the findings.

F. References

2. Quigley C. Opioids in people with cancer-related pain. *Clin Evid (Online)* 2008; 2008.

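### The IV-versus-FSS contrast sets an unselected IV episode against an FSS record chosen because pain fell, so it favours FSS even if the treatments are identical

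*Combined protocol and SAP*

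**What the plan says.** - **The contrast.** Secondary objective #1 (section A) compares IV opioid "breakthrough and FSS at effective dose". Section D.1 repeats it as a secondary endpoint: "differences in the pain response between intravenous opioid breakthrough and FSS at effective dose".
- **The IV record.** Section C.4, Stage 1 item (1) gives, for the first episode, a "single dose of breakthrough opioid from their existing PCA pump that is equivalent to 10% of their MEDD". Table 3 scores pain at 0, 15 and 30 minutes. No response condition applies.
- **The FSS record.** Stage 1 item (2)a calls a dose effective if pain falls by at least 2 points, falls by at least 33%, reaches the personal pain goal or lower, "OR absolute value below background pain level will be considered as an effective dose". Sections C.1 and C.4 allow up to four FSS doses over two episodes to meet this.
- **When scoring stops.** Table 3, footnote 10: "Breakthrough pain episode #3 will only be assessed if the patient did not achieve an effective dose after the first FSS dose". Stage 1 item (6): "Once the effective dose is found, the first stage of this study is complete and they will no longer be on FSS".
- **Other analyses.** D.2 summarises "the changes of pain score after each episode" and permits a repeated-measures model with a treatment effect. D.1 also reports the percentage treated with FSS who never reach an effective dose. Neither is named as the analysis for secondary objective #1.

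**The concern.** The rule that picks the FSS record uses the same quantity that is then compared. An FSS episode with a poor response is passed over, and the patient gets another chance; an IV episode with a poor response stays in. Relief varies from one episode to the next, so the chosen FSS record carries favourable chance variation and the IV record does not. On the responder scale FSS is 100% by construction, while IV is free to fail.

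Nothing later in the study repairs this. Stage 1 ends once a dose has worked, so no further in-hospital episode at that dose is scored free of the selection. Stage 2 collects a daily 24-hour average, not a 30-minute response. Patients who never respond have no FSS value to enter.

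The plan states no hypothesis test here, so the harm is a misleading estimate. Section B says the preliminary data will serve to design a randomized FSS-versus-IV trial. The plan does not name this difference as the effect size for that trial, but nothing warns against using it so.

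**Working it through.** **The plan's own figures.** D.1 gives no precision or effect size for this objective. Its figures concern the primary objective and reproduce: 30 × 0.75 = 22.5, stated as 22; and 1.96 × 5 / √22 = 2.09, stated as 2.1%. They neither support nor weaken the point.

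**Set-up.** Suppose IV and FSS are identical. Each patient has three exchangeable episodes (IV, FSS 1, FSS 2) with the same mean 30-minute fall, SD and within-patient correlation. The FSS value is the first FSS episode with a fall of at least 2 points, paired with that patient's IV value. The true difference is zero, so any non-zero average is bias.

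**Assumed inputs** (not in the documents): mean fall 1.5, 2, 2.5 or 3; SD 1.5 or 2; correlation 0, 0.25 or 0.5.

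**Closed form at correlation 0.** With a = (2 − mean)/SD:

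bias = SD × φ(a) / (1 − Φ(a)); proportion responding within two episodes = 1 − Φ(a)².

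| Mean | SD | a | Bias (points) | Responding |
|---|---|---|---|---|
| 1.5 | 2 | 0.25 | 2 × 0.3867 / 0.4013 = 1.93 | 1 − 0.5987² = 64% |
| 2 | 2 | 0 | 2 × 0.3989 / 0.5 = 1.60 | 1 − 0.5² = 75% |
| 3 | 1.5 | −0.67 | 1.5 × 0.3194 / 0.7475 = 0.64 | 1 − 0.2525² = 94% |

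**Full grid** (simulation, 2 million patients per cell):

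- The bias runs from 0.37 (mean 3, SD 1.5, correlation 0.5; 88% respond) to 1.93 (first row above). With whole-number scores it is 0.27 to 1.63.
- D.1 expects that "22 patients are expected to be treated with FSS and reach the effective dose measured as % MEDD dose", out of 30, or 73%. In cells with at least 73% responding, the bias is 0.37 to 1.60.
- With all four effectiveness criteria on a whole-number scale, it is 0.22 to 1.31 with a repeat dose adding half the effect, and 0.24 to 1.46 without a repeat. This further assumes baseline pain 4–9, background 0–3 and personal goal 1–4, all uniform, and correlation 0 or 0.5.
- Limiting cases: 0.05 when nearly every dose works (mean 5, SD 1.5, correlation 0.5) and 0.01 at correlation 0.99.
- First FSS dose minus IV, responders or not, averages 0.00 in every cell.

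**A second, differently built simulation** used between-patient SD 1, within-patient SD 0.5 to 2, mean fall 1.5 to 3, whole-number scores, baseline about 6, and 3/10 standing in for background and goal. With two chances the bias was 0.06 to 1.42, always toward FSS; with four chances, 0.07 to 1.50. In the patients selected, IV met the same response rule in 56% to 94%, against 100% for FSS. With 22 pairs and the 2-point rule alone, a paired 95% interval lay wholly on the FSS side in 20% to 75% of simulated trials across the five settings tried, against a nominal 2.5%.

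**What drives it.** Restricting which patients enter does not by itself bias a paired difference. Choosing the FSS episode by its result does.

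**The case against.** The strongest reply is that D.2 already allows a sound analysis. It lets each endpoint be evaluated at each episode and a treatment effect be estimated in a repeated-measures model. Such a model, fitted to every scored episode, is not distorted by this rule, because whether the third episode is scored depends on an observed response. In two simulated null settings a random-intercept model gave −0.003 (SE 0.016) and −0.019 (SE 0.010), where the selected contrast gave +1.26 and +0.67. This stands as far as it goes. But D.2 makes the model optional and does not say which FSS records or time points serve this objective, while sections A and D.1 name the selected contrast.

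Four further points have weight:

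- The four criteria are joined by OR, so the real rule is easier to meet than the 2-point criterion alone, and the lower range (about 0.2 to 1.5) is nearer to the protocol. The 73% in D.1 also counts withdrawals and drop-outs, so response among FSS-treated patients should be higher and the bias smaller. The largest values need zero within-patient correlation.
- The direction is established for the selection component only. Fixed IV-first order, open-label rating, unequal proportions of MEDD and possible 60-minute FSS scores also act on the contrast, and their net effect cannot be derived from the documents.
- D.1 names the effective dose, not this difference, as the quantity for powering later studies. Use of the difference as an effect size is a risk, not a stated plan.
- The objective asks about the titrated dose, and a first-dose contrast answers a different question. That is a real cost. But Stage 1 scores no further episode at the dose found effective, so it cannot give an effective-dose comparison free of selection on the same record.

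**Conclusion.** The concern holds, and the contrast is wrong as written. That the selection favours FSS follows from the documents, given that relief varies between episodes and some doses fail. The size does not follow from them. Under the stated assumptions it is about 0.2 to 1.5 points with all four criteria and 0.37 to 1.93 with the 2-point criterion alone, close to zero only in the limiting cases. For scale, the protocol counts a 2-point fall as an effective response. The matter should be fixed, but it is confined to a secondary estimate in a 30-patient preliminary study; the primary objective is not affected.

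**What to change.** Amend sections A, D.1 and D.2 as follows.

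1. Make the main estimate for secondary objective #1 the within-patient difference in pain change from 0 to 30 minutes: first FSS dose (second episode) minus IV dose (first episode). Include every patient who received both, whether or not an effective dose was found, and report the mean difference with a paired t 95% confidence interval.
2. Report the 30-minute responder rate for each treatment, applying the criteria of Stage 1 item (2)a to both.
3. Keep the effective-dose contrast as descriptive, label it 'selected on response', and state that it will not be the effect size for the next trial.
4. State that fixed order, open label and different proportions of MEDD (IV 10%, FSS 16–32%) remain, so the result is not a pure drug or route effect.

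**Cost.** No new data: Table 3 already schedules 0- and 30-minute scores for both episodes. The change is in wording, though it touches a stated objective. The main contrast will describe the FSS starting dose instead of the titrated dose, and it will look less favourable to FSS.

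**Expected precision**, with SD 1.5 to 2 and correlation 0 to 0.5 assumed and SD of the difference = SD × √(2(1 − correlation)):

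- 22 pairs, SD 2, correlation 0: 2.080 × 2.83 / √22 = ±1.25 points.
- 30 pairs, SD 1.5, correlation 0.5: 2.045 × 1.5 / √30 = ±0.56 points.
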